Data source(s)	
Patients' demographic and clinical data will be sourced from patients' medical records and other systems within the main (specialist) participating FD centres and extracted into electronic case report forms (eCRFs).
 
For the time and motion component of the study, prospective data relating to HCP time associated with the preparation and administration of a single dose of ERT will be captured by direct observation of HCPs by an independent external researcher or a member of the patients' care team, during the episode of care and recorded on a paper case report form (CRF) which will then be transcribed into an eCRF.
 
Patient- and caregiver-reported outcomes will be reported directly by patients and caregivers using anonymised-coded paper-based questionnaires which will be transcribed into an Excel database by central data managers.

Study time period(s)	
It is anticipated that the prospective recruitment / data collection period for this study will be approximately 4-5 months, starting from the date on which the relevant approvals to conduct the study are in place. A maximum of three episodes of care per patient during the data collection period will be included. Consenting patients with FD and their caregivers will be asked to complete the study questionnaires at the time points described above.

Study endpoints	Primary endpoint: Summary measures of the total time spent by HCPs in the preparation and administration of a single dose of ERT in patients

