
 ○ Infusion (and pre-medication) preparation activities. ○ Administration of ERT (and pre-medications). ○ Monitoring of patient during and after administration. ○ Completion of clinical documentation. ○ Any other ERT-administration related activities. ● Distribution of the roles of HCP (physician / nurse / nurse assistant or healthcare assistant / pharmacist / pharmacy assistant / other) involved in each task. ● Summary measures of the ERT dose administered. 	
 ● Activities associated with the preparation and administration of ERT: ● Pre-administration patient consultation: 
 ○ Time patient arrived in clinic room. ○ Time patient left clinic room. ○ Start and end time of patient consultation with HCP for pre-treatment assessment. ○ Start and end time of prescription writing (if additional to consultation time with patient). ○ Start and end time of pre-administration clinical documentation (if additional to consultation time with patient). ○ Role of HCP(s) involved (physician / nurse / nurse assistant or healthcare assistant / other [specify]). ● Infusion (and pre-medication) preparation activities: 
 ○ Start and end time of infusion (and pre-medication) preparation activities (note: the following activities [as appropriate] will be included
---	---

	
in the total time, but the time for each separate activity will not be recorded]: pre-dispensing prescription review, label generation, collation of items prior to assembly, assembly of item/drug reconstitution, labelling of containers, accuracy check, prescription delivery).
 
○ Role of HCP(s) involved (physician / nurse / nurse assistant or healthcare assistant / pharmacist / pharmacy assistant / other [specify]).● ERT (and pre-medication) administration:
○ Time patient arrived in clinic for ERT administration○ Time patient left clinic following ERT administration○ Start and end time of pre-medication administration.○ Start and end time of ERT infusion.○ Start and end time of HCP activity for administration of IV agalsidase alfa or agalsidase
--	---

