agalsidase beta) in each participating country. Ideally, a maximum of two ERT administration episodes will initially be observed per patient (except in exceptional cases where it is determined that it is required to observe three episodes per patient due to a limited number of available patients/episodes for observation), and at least 30 patients are expected to be enrolled in each country. For countries with limited FD patient numbers, a review of episodes of care observed will be completed on an ongoing basis. It may be determined that it is possible to observe three episodes per patient in these circumstances, however only two episodes will be observed per patient wherever possible.

For the questionnaire evaluation, approximately 120 patients and 20 caregivers will be expected to fill questionnaire sets (approximately 30 patients' and 5 caregivers' questionnaire sets per country).

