Data management for eCRFs will be carried out using MACRO™, a data management system which has a secure web-based data entry interface and is fully validated and compliant with Food and Drug Administration (FDA) Information Governance standard 21 Code of Federal Regulations (CFR) Part 11. The MACRO™ system has restricted access, role-based permissions for data entry management and analysis and maintains an audit trail of all changes to data and activity in the system in line with 21 CFR Part 11. Members of the whole care team and external researchers will be trained in data entry into the eCRFs by study management staff from Open Health. Entry to MACRO™ will be restricted (by password protection) to only those members of staff directly involved with the study.

Consenting patients and caregivers will be given the relevant paper-based patient- and caregiver-reported outcome measures to complete either during the visit to the hospital or treatment centre for administration of ERT or at home after leaving the clinic (as described above). Completed questionnaires will be handed back or posted (using a pre-paid envelope) to the hospital or treatment centre staff or, alternatively, responses to the questionnaires completed by patients and caregivers after leaving the clinic (bespoke questionnaire, second and third bespoke fatigue Likert scale and first WPAI questionnaire) may be collected over the telephone during a call with a member of the patient's care team. The hospital or treatment centre staff will forward the completed questionnaires to the study management company for entry into a bespoke study database in Microsoft Excel™. Entry to the study database will be restricted (by password protection) to only those members of staff directly involved with the study.

Data will be prepared for analysis using R statistical software version 3.4.1, Stata™ (StataCorp LLC) version 14 and/or Microsoft Excel™. Data management and handling of data will be conducted according to the study-specific data management plan (DMP).

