9.10 Quality control

All staff collecting data for the study (site staff and/or external observers) will be provided with data collection guidelines and will receive training in the requirements of the study protocol and correct data collection. This will ensure consistent completion of the eCRF for demographic information, paper CRF for time and motion data collection, and administration of paper questionnaires to patients and caregivers.

Data collection for the prospective time and motion study will be performed by trained external observers from the study management company or by members of the patients' care team at each site, who will also receive training in the time and motion study procedures. The observers will record start and stop times for each task on paper CRFs. It is recommended that 2 timing devices are used in case of failure of one of the devices. For the purposes of quality control, each data collector will transcribe the first 3 completed CRFs into the eCRF within 1 business day of the data collection and the entered data will be reviewed by project management or data management staff from the study management company. If errors or inconsistencies in the data are noted, additional training will be provided to the observers.

This pilot exercise will also be used to confirm that the database and CRF have been designed appropriately and that the data collection methodology is feasible.

Data collection progress will be monitored by local Clinical Research Associates (CRAs) on an ongoing basis and support will be available throughout the entire study period to observers and site study staff as required.

Patient demographic data and data submitted for the time and motion component of the study will be checked for completeness and accuracy by the Open Health data management team using agreed manual and programmed validation checks, which will be specified in the study DMP. Missing values may occur during collection of observational data (e.g. due to stopwatch failure). The frequency of these missing values will be tabulated as part of the data analysis but no queries will be raised. Other queries related to out-of-range values, inconsistent responses and any other data issues will be raised with each site by the data management team at the study management company, and resolutions documented. Study centres will be required to co-operate with the data management team in the resolution of these queries.

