No queries will be raised on patient- or caregiver-reported data.

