9.11 Limitations of the research methods

- Patient and caregiver consent is a requirement of this study; this may introduce selection bias and result in a study sample that may not be representative of the wider patient and caregiver population of interest.
- Centres will be selected on the basis of interest in taking part in the study and experience in treating patients with FD with ERT. It is acknowledged that these centres may not be representative of current wider clinical practice in the countries of study.
- For patient- and caregiver-reported outcomes, the data will rely on the completeness of the answers provided by participants, which will not be queried or otherwise followed up to clarify inconsistencies or omissions and may be subject to reporting bias.
- A limitation of asking patients to complete questionnaires during their ERT infusion is that they may feel more anxious and/or tired when they are attending the hospital to receive treatment than at other times; consequently, the descriptions of patient-

reported HRQoL and general wellbeing obtained in the study may be an overestimate of the overall impact of FD.

- This is a descriptive study and no analyses to control for confounding will be carried out. For ethical reasons, time and motion data will not be stratified by individual staff member, although the performance of staff may be a factor in any observed variability. Experience levels of staff performing tasks observed in the study may vary between centres and may not reflect the experience level of staff performing the same tasks outside the study centres. There are also likely to be differences between the participating countries in local clinical protocols, healthcare settings and care processes, which may introduce variability in the data collected.
- It is acknowledged that the time and motion evaluation may not capture the full burden of ERT administration since first infusions (which are expected to take longer than subsequent infusions) are excluded from the study; this is because the longer first infusion represents only a one-off burden at the start of long-term (potentially lifelong) treatment.
- It is also acknowledged that QoL data could be impacted by ERT episodes that are close in timing to each other.

10. Other aspects

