10.1 Review of study results

Analysis of the primary endpoint, the total time spent by HCPs in the preparation and administration of a single dose of ERT in patients with FD, will be independently reviewed by a member of the Data Analysis team at Open Health who was not involved in the analysis of the final study data. No additional analysis checks will be carried out.

It is anticipated that study results will be presented to investigators to enable a preliminary discussion of the results of the study, at a meeting to be planned after completion of the data analysis and before the study report is prepared.

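### No stated check stops impossible or out-of-order patient and caregiver clock times from entering the means and SDs of total time, which are main secondary endpoints

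*Protocol*

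**What the plan says.** The protocol's abstract lists summary measures of total patient time and total caregiver time among the main secondary endpoints. Table 4 (Protocol 9.6) builds them from times that the respondent records: leaving home or work, arriving at the centre, start of infusion, leaving the centre and arriving back, with further times when the infusion is given at home. SAP 2.6 takes differences between pairs of these times in minutes and summarises each one.

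The abstract says the paper forms hold responses "which will be transcribed into an Excel database by central data managers". Protocol 9.9.1 likewise has site staff "forward the completed questionnaires to the study management company for entry into a bespoke study database", and allows some answers to be taken by telephone.

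The stated safeguards are these:
- Protocol 9.10: "Patient demographic data and data submitted for the time and motion component of the study will be checked for completeness and accuracy". These are the manual and programmed checks, and questionnaire data are not named. The same section adds "No queries will be raised on patient- or caregiver-reported data".
- Protocol 9.11 lists as a limitation that the respondents' answers are data "which will not be queried or otherwise followed up to clarify inconsistencies or omissions".
- Protocol 10.1 and SAP 3.2 give independent review to the primary endpoint (HCP time) and then state "No additional analysis checks will be carried out".
- Protocol 9.9.3 and SAP 2.3 impute partial dates and otherwise analyse whatever data are available. Neither has a rule for a value that is present but impossible.

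Protocol 9.8 expects "approximately 30 patients' and 5 caregivers' questionnaire sets per country".

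**The concern.** Choosing not to go back to patients is defensible. It does not settle what the analyst should do with a form on which the patient leaves home after arriving at the centre. The plan names no step at which such a form would be caught, and no rule for handling it. The value then either enters the mean and SD, or is removed ad hoc once the country and product results are visible.

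These times are the study's measure of the burden on patients and families, and the abstract says the data may go into HTA submissions. The groups are small, and caregiver groups very small, so one gross error can carry weight.

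The sign of an interval cannot be relied on as a flag either. Read literally, some SAP 2.6 formulas subtract the later time from the earlier (outbound travel; arrival to start of infusion), while the homeward journey is subtracted the other way round. Correct data would then give negative values for some intervals.

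**Working it through.** **Inputs from the documents.** About 30 patient and 5 caregiver sets per country (Protocol 9.8). Over four countries, 4 × 30 = 120 and 4 × 5 = 20, which reproduces the stated totals. The documents give no figure for the effect of a wrong time.

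**Assumptions.** The error size is mine: 10 minutes to 12 hours, the top being an am/pm slip. The figure of 15 patients per country and product assumes that the 30 split evenly.

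**Shift in the mean.** One error of size e among n values moves the mean by e/n (minutes):

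| Error e in one leaving-home or arriving-home time | n = 30 patients | n = 15 patients | n = 5 caregivers |
|---|---|---|---|
| 10 min | 0.3 | 0.7 | 2 |
| 1 h (60) | 2 | 4 | 12 |
| 2 h (120) | 4 | 8 | 24 |
| 10 h (600) | 20 | 40 | 120 |
| 12 h (720) | 24 | 48 | 144 |

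Pooled over countries, a 1-hour and a 12-hour error give 60/120 = 0.5 and 720/120 = 6 minutes for patients, and 60/20 = 3 and 720/20 = 36 minutes for caregivers. To move a mean by more than 20 minutes, the error must exceed 20n: 600 minutes at n = 30, 300 at n = 15 and 100 at n = 5.

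**Which times matter.** If the total is last time minus first, or the sum of adjoining segments, each intermediate time enters once with a plus and once with a minus and cancels. Only the leaving-home and arriving-home times then move the total. SAP 2.6 gives no explicit formula for the total, so this is a condition. Intermediate errors still distort the intervals that SAP 2.6 reports separately: a wrong arrival time, for example, alters both outbound travel and the wait for infusion.

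**Spread.** An error e in one of n values adds e²/n to the expected sample variance. For n = 30 and e = 720 this is 720²/30 = 17,280. The true SD is not in the documents, so I show a range:
- SD 31.25: √(976.6 + 17,280) = 135, a factor of 4.3
- SD 60: √(3,600 + 17,280) = 144.5, a factor of 2.4
- SD 90: √(8,100 + 17,280) = 159, a factor of 1.8

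The 95% interval widens by the same factor. A 1-hour error adds only 3,600/30 = 120, so at SD 60 the SD becomes √3,720 = 61.

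**Median.** In simulated normal data, a 12-hour error in one of 30 values moves the median on average by 1.3 minutes (SD 31.25) to 3.8 minutes (SD 90). With n = 5 and SD 90 it moves by about 27 minutes.

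**The case against.** The case for leaving the plan alone has substance:
- **It is deliberate and disclosed.** Protocol 9.11 owns the limitation, the study is descriptive, and the primary endpoint is both queried and independently reviewed. This stands, and it limits the importance of the point.
- **Robust summaries are planned.** Medians, IQR and range accompany the means (Protocol 9.9.2, SAP 2.5). A 12-hour error barely moves a 30-patient median, and an extreme or negative value would show in the range. That protects patients well and five caregivers poorly. Seeing a bad value in the range also does not say what to do with it.
- **The data management plan is not among the documents** and may contain entry checks. That is possible. However, Protocol 9.10 refers to that plan for validation of the other data only, and a rule that decides which values are analysed belongs in the SAP.
- **Independent review of analysis code might not catch am/pm errors.** Agreed. The missing step is a data check more than a second analyst.

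A reader might infer that the observers' records can repair these data, since Table 4 has the observer record items such as "Time patient left clinic following ERT administration". The documents do not support that. Patients may join only one component (Protocol 9.3), and the questionnaire visit need not be an observed one. Observers record no home times and no caregiver times, and infusions run at home are timed by the patient (Protocol 9.2). The observer notes arrival in the clinic, whereas the form asks about arrival at the hospital or treatment centre. Substituting one for the other could drop registration and waiting time that the endpoint includes.

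**Conclusion.** The gap is real and follows from stated policy. Validation, queries and independent review each stop short of patient- and caregiver-reported times, and SAP 2.3 has no rule for an impossible one. Under the assumed errors of 1 to 12 hours, one wrong home time moves a country mean by 2 to 24 minutes for 30 patients and by 12 to 144 minutes for 5 caregivers. Caregiver means by country are the most exposed, if they are reported at all: Protocol 9.9.4 makes stratified secondary analyses conditional on sufficient numbers.

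A reader might infer that any single slip moves a country's patient mean by more than 20 minutes. It does not. At n = 30 that takes an error above 10 hours in a leaving-home or arriving-home time, and a 1-hour error moves the mean by 2 minutes. The documents give neither the size nor the frequency of such errors, and the questionnaire's clock format is not visible.

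The result rests on the assumed error sizes, the planned numbers being reached, an even product split for n = 15, and the total being computed so that intermediate times cancel. I class this as a cheap improvement to secondary endpoints.

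**What to change.** Add to SAP 2.3:
1. A programmed order and range check on every bespoke patient and caregiver form: left ≤ arrived ≤ infusion start ≤ left centre ≤ back, adapted to the home-infusion sequence, with a prespecified maximum for each interval and for the total. Apply it to the clock times themselves, and provide for a genuine return after midnight.
2. Compare each failing value with the paper form, or with the record of the telephone call, and correct keying errors.
3. If the value is still impossible, set the affected interval to missing, together with any total that depends on the wrong time. Allow no partial sums, which would bias totals downwards.
4. Report the number of values corrected and set to missing, by country and product.
5. Where a form and an observed episode share patient and date, use the observer's clinic and infusion times as a plausibility check only, never as replacements.

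State the formula for the total in SAP 2.6 at the same time, and write every interval as later time minus earlier.

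The cost is a short script, a paragraph of SAP text and a few intervals becoming missing. No patient or caregiver is contacted, so the no-query policy stands. The check catches gross errors that break the order or exceed the maximum. A 1-hour error that does neither will remain, at 2 minutes on a 30-patient mean and 12 minutes on a 5-caregiver mean, so the median should be shown beside every caregiver mean.

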9.11 Limitations of the research methods

- Patient and caregiver consent is a requirement of this study; this may introduce selection bias and result in a study sample that may not be representative of the wider patient and caregiver population of interest.
- Centres will be selected on the basis of interest in taking part in the study and experience in treating patients with FD with ERT. It is acknowledged that these centres may not be representative of current wider clinical practice in the countries of study.
- For patient- and caregiver-reported outcomes, the data will rely on the completeness of the answers provided by participants, which will not be queried or otherwise followed up to clarify inconsistencies or omissions and may be subject to reporting bias.
- A limitation of asking patients to complete questionnaires during their ERT infusion is that they may feel more anxious and/or tired when they are attending the hospital to receive treatment than at other times; consequently, the descriptions of patient-

reported HRQoL and general wellbeing obtained in the study may be an overestimate of the overall impact of FD.

- This is a descriptive study and no analyses to control for confounding will be carried out. For ethical reasons, time and motion data will not be stratified by individual staff member, although the performance of staff may be a factor in any observed variability. Experience levels of staff performing tasks observed in the study may vary between centres and may not reflect the experience level of staff performing the same tasks outside the study centres. There are also likely to be differences between the participating countries in local clinical protocols, healthcare settings and care processes, which may introduce variability in the data collected.
- It is acknowledged that the time and motion evaluation may not capture the full burden of ERT administration since first infusions (which are expected to take longer than subsequent infusions) are excluded from the study; this is because the longer first infusion represents only a one-off burden at the start of long-term (potentially lifelong) treatment.
- It is also acknowledged that QoL data could be impacted by ERT episodes that are close in timing to each other.

10. Other aspects

10.1 Review of study results

Analysis of the primary endpoint, the total time spent by HCPs in the preparation and administration of a single dose of ERT in patients with FD, will be independently reviewed by a member of the Data Analysis team at Open Health who was not involved in the analysis of the final study data. No additional analysis checks will be carried out.

It is anticipated that study results will be presented to investigators to enable a preliminary discussion of the results of the study, at a meeting to be planned after completion of the data analysis and before the study report is prepared.

